6.4 Data documentation

Each data file will have an associated data dictionary that will be developed and vetted by the relevant study partners (i.e., the originator and users of each data file).

Data dictionaries to be developed will include the following data files: clinic data identifying care coordination patients, care quality data from MNCM, utilization data from each participating payor, interview/survey data for each administered interview/survey, and the final de-identified research analytic files. Where appropriate, metadata standards will also be collaboratively developed.

6.5 Data storage and preservation

HPI's networked workstation computers communicate with the larger HealthPartners (HP) corporate network. Data systems for storing and backing up data reside both at the HP corporate headquarters and in a secure offsite facility. Data are backed up daily, weekly and monthly. Computer and data needs are supported by the larger organization's Information Systems & Technology Department, which maintains all HP computer hardware, software and data, including electronic medical record, research, and administrative data.

Interview data is preserved for recovery by saving it in several forms: audio, raw transcripts, and clean transcript. Audio and raw transcript files are maintained with the transcription company, and can be re-downloaded at any time in the event of a file loss.

6.6 Data maintenance

Final de-identified study data, documentation, metadata, and analytic files will be maintained in a study-specific file folder using widely used file formats (e.g., text delimited files, PDFs, Microsoft Word documents, and SAS/R programs) that will require minimal maintenance during the course of the study or in the future. We do not have infrastructure to support a data repository for qualitative data at this time.

6.7 Data sharing

The project team outside of the data analysts will view data primarily as summaries, but will have full access to the clean and de-identified data sources. Other stakeholders will primarily interact with high level summaries of findings in manuscripts, presentations, and/or reports.

Individual consent to participate in the interviews assured participants that their information will not be shared on an identifiable individual level. We will not make identifiable individual level interview data or meeting notes available to stakeholders outside our study team, consultants named in the consent, and the outside transcription service. Regulatory bodies named in the interview consent forms will be able to access primary de-identified data for examination upon request.

To facilitate the conduct of future research, we will create de-identified data sets from the completed project in a manner consistent with human subject protection and HIPAA privacy regulations. These data sets will be kept at HPI along with data dictionaries, coding manuals, and other documentation

relevant to data collection or measurement issues. These resources will be available to the funding agency or to other approved investigators according to requirements imposed by the governing IRB and legal requirements, including HIPAA and DUAs, and organizational and/or technical constraints.

6.8 Masking

When possible, clinic and comparator identities will be masked from the study team until the primary analyses are completed, but strict masking will not be possible due to the mixed methods used for data collection (i.e., the combination of qualitative and quantitative data) and due to data attributes that are known a priori (e.g., the number of clinics associated with a care system or a care coordination model).⁴⁷

7 Statistical Analysis Plan

This observational study will use a mixed-method convergent design,⁴⁷ including exploratory and explanatory evaluation of the comparative effectiveness of two care coordination models implemented by up to 397 adult primary care clinics certified as HCH by MDH. For quantitative inferential analysis of each aim, standard multivariable generalized linear mixed effects regression models (GLMMs) will be constructed for each study outcome, using SAS (v9.4) and/or R (v4.1.2) analytic software. Causal inference will be informed by the PICOTS framework.⁴⁸ Descriptive analyses will include summaries (means, standard deviations, counts, proportions) of baseline characteristics of the study population along with tests of bivariate association (e.g., Fisher's exact test, Kruskal-Wallis, as appropriate) between patient, clinic, and contextual factors and the care coordination comparator, survey response, or study outcomes. Aims 2 and 3 will incorporate qualitative data obtained via patient surveys and clinic interviews. Qualitative findings will enhance understanding of the quantitative findings and our ability to address additional research questions raised by patients, partner organizations, and community stakeholder groups. We will follow the Strengthening the Reporting of Observational Studies in Epidemiology (STROBE) reporting guidelines to help ensure sufficient information in reports to allow for assessments of the study's internal and external validity.⁴⁹

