7.3 Analysis Plan

7.3.1 Aim 1 Analysis

To evaluate the impact of coordination type (medical/social vs. nursing/medical) on study outcomes, we will specify a series of generalized linear mixed models (GLMMs). Individual patients (nested within clinic and organization) are the primary unit of analysis. To account for patient clustering, we will incorporate a random intercept for clinic into the model. Covariates will be specific to a given model (outcome) and will be selected based on a combination of substantive knowledge, empirical evidence, and model fit statistics (e.g., Bayesian Information Criterion). Investigators will first select a set of covariates that must be included in each model. From this initial set, a forward stepwise selection algorithm will select additional covariates to include until a stopping criterion is met, and the final model specification for each outcome is identified.⁵² Random effects will be evaluated and retained in a given model based on model fit statistics and Wald tests for covariance parameters. Patient care quality outcomes for Aim 1 analyses will be modeled as binary dependent variables (e.g., meeting goal vs. not meeting goal) within subgroups based on a patient's status at the time of care coordination initiation (e.g. meeting criteria at the start of care coordination vs. not), and corresponding GLMMs will have the general form:

$$(1) \eta_{ijk} = \gamma_{000} + u_{0j0} + \gamma_{100}X_{ijk} + \gamma_{010}CC_{jk} + \gamma_{020}W_{jk} + \gamma_{001}Z_k + \varepsilon_{ijk}$$

where η represents the log-odds of a care quality outcome (e.g., BP control); γ_{000} is the intercept (value for a 'typical' patient at a 'typical' clinic); u_{0j0} is the random intercept at the clinic level; X_{ijk} is a vector of covariates (age, etc.) for patient i within clinic j and organization k ; CC_{jk} represents the exposure variable of interest, care coordination type, designated at the clinic level; W_{jk} is a vector of clinic-level covariates; and Z_k is a vector of organization-level covariates. Effect estimates will be calculated via γ coefficients (specifically γ_{010} for the relative log-odds comparing the medical/social vs. nursing/medical care coordination model); ε_{ijk} is an error term. In addition to analyses of individual care quality

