7.3.3 Aim 3 Analysis

Identification of significant organization, care process, and patient factors will be embedded in analyses for Aims 1 and 2 and will be represented as covariates in final selected models for study outcomes. Whereas Aim 1 analyses seek to quantify effect estimates for $\gamma_{010}CC_{jk}$ in equation 1 above, for Aim 3 we intend to quantify γ coefficients for patient-level factors X , clinic-level factors W , and organization-level factors Z . As described above, we will iteratively optimize models using a forward stepwise selection algorithm. Summaries for unadjusted and adjusted comparisons for all variables under study will be tabulated and/or plotted accordingly. Again, Aim 3 analyses will be conducted separately for the Primary and Historical cohorts as described above.

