7.3.8 Bias Mitigation

To mitigate bias, we will: 1) rely on subject area experts on our project team and in the clinics to identify anticipated confounders for the relationship(s) between coordinated care model and study outcomes; 2) use directed acyclic graph methods to diagnose potential sources of confounding or selection bias, and identify analytic approaches to correct such biases⁶¹; 3) evaluate imbalances in empirical distributions of covariates with respect to care coordination model, and their associations with study outcomes (requisite criteria for presence of confounding); 4) employ appropriate analytic strategies (stratification, multivariable modeling, inverse probability weighting)⁶²; 5) conduct sensitivity or quantitative bias analyses to calculate reasonable bounds for study estimates under varying assumptions⁵⁷; and 6) acknowledge remaining limitations to be considered when interpreting our study results.

8 Qualitative Analysis Plan

Drs. [name], [name], and [name] in consultation with [name] will lead the qualitative data analysis of participant interviews. Qualitative data analysis will be approached from two perspectives: at baseline for survey development (Phase 1) and again in the final year (Phase 2) to understand meaning, implications, and recommendations regarding the study findings from the perspectives of patients, care coordinators, and clinicians/leaders.

In Phase 1 patient, clinician/leader, and care coordinator interviews, we will first conduct a rapid analysis of any content that needs to be incorporated in the subsequent surveys of being developed for patients or care coordinators, which will be followed by a more deliberative directed content analysis approach. Following interview completion, audio recordings will be transcribed using a professional transcription service. These transcripts will be discussed by the analysis team as they are completed in order to identify immediately actionable information regarding survey development. Then, interview

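### The bivariate tests in Section 7 make no allowance for clustering by clinic; run on patient rows against a clinic-level variable, a nominal 5% test has a true size of about 12 to 13% at the plan's own ICC in the full cohorts.

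*Combined protocol and SAP*

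**What the plan says.** The opening paragraph of Section 7 (Statistical Analysis Plan) separates inference from description. Inference is by mixed model: "For quantitative inferential analysis of each aim, standard multivariable generalized linear mixed effects regression models (GLMMs) will be constructed for each study outcome". Description is introduced with "Descriptive analyses will include summaries (means, standard deviations, counts, proportions) of baseline characteristics of the study population" and is accompanied by bivariate tests, the named examples being Fisher's exact and Kruskal-Wallis: "exact test, Kruskal-Wallis, as appropriate) between patient, clinic, and contextual factors and the care coordination comparator, survey response, or study outcomes". Nothing is said about the unit of analysis for these tests or about clustering.

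Clustering is recognised elsewhere. Sections 7.2.1 and 7.2.2 assume an ICC of 0.01. For the Aim 1 models, Section 7.3.1 says "Individual patients (nested within clinic and organization) are the primary unit of analysis" and that "we will incorporate a random intercept for clinic into the model". Sections 7.3.6.3 and 7.3.6.5 state that the care model is chosen and implemented by the clinic.

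Two later sections could draw on bivariate results. Section 7.3.8, item 3, will "evaluate imbalances in empirical distributions of covariates with respect to care coordination model, and their associations with study outcomes (requisite criteria for presence of confounding". Section 7.3.3 promises: "Summaries for unadjusted and adjusted comparisons for all variables under study will be tabulated and/or plotted accordingly". Neither names a test or a p-value rule.

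**The concern.** Fisher's exact and Kruskal-Wallis take their null distribution from independent observations. Patients in one clinic share a care model, a catchment population and a care team, so for any comparison in which one variable is constant within a clinic, the effective sample is smaller than the patient count. The p-value is then too small.

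Several of the listed pairings are of that kind if patients are the rows: patient factors against the care model, and clinic factors against survey response or outcomes. At stake are the p-values in the balance table, the comparison of survey responders with non-responders, and any unadjusted tests of clinic factors. Section 7.3.6.5 forgoes propensity scores for the primary analyses and relies on covariate adjustment, so readers will look closely at the balance table. It also expects remaining imbalances to reflect differences between clinics in the patients they serve, which is the situation in which patient-level tests mislead.

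**Working it through.** **Inputs.** Section 7.2.1: about 397 clinics split 55:45, 57 patients per clinic, 45% with claims data, 7,000 surveys at 60% response, ICC 0.01, two-sided alpha 0.05. Section 7.2.2: 66 patients per clinic in the Historical Cohort.

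**The plan's own figures.** Claims: 57 × 0.45 = 25.7, stated as 26. Survey: 7,000 × 0.60 = 4,200; 4,200/397 = 10.6 and 4,200/(0.75 × 397) = 14.1, stated as about 10 or 14. With the design effect DEFF = 1 + (m − 1) × ICC, the detectable difference on the PROMIS score (SD 10) with all clinics and m = 10 is 2.80 × 10 × √[(1.09/10) × (1/218.35 + 1/178.65)] = 0.93, in line with the stated 1 point. The plan's sample-size reasoning therefore fits an ICC of 0.01 with these cluster sizes.

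**True size of an unadjusted test of a clinic-level variable.** Size = 2 × [1 − Φ(1.96/√DEFF)], equal clinic sizes, ICC 0.01:

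| Rows used | m | DEFF | True size |
|---|---|---|---|
| Survey respondents, all clinics | 10 | 1.09 | 6.0% |
| Survey respondents, 75% of clinics | 14 | 1.13 | 6.5% |
| Claims, Primary Cohort | 26 | 1.25 | 8.0% |
| All patients, Primary Cohort | 57 | 1.56 | 11.7% |
| All patients, Historical Cohort | 66 | 1.65 | 12.7% |

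A test of survey response itself would use everyone sent a survey: 7,000/397 = 17.6 or 7,000/(0.75 × 397) = 23.5 per clinic, giving DEFF 1.17 or 1.23 and a size of about 7 to 8%, if response also has an ICC of 0.01.

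**Simulation of the two named tests.** With no true difference, 397 equal clinics and 1,000 runs per setting, Fisher's exact and Kruskal-Wallis rejected in 5.3% and 6.2% of runs at m = 10, 8.9% and 8.5% at m = 26, and 12.7% and 10.8% at m = 57. The formula holds within simulation error (about 1 percentage point at m = 57).

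**Stronger clustering (assumed; the documents give no ICC for baseline factors).** At m = 57, ICC 0.05 gives DEFF 3.80 and 31%; ICC 0.10 gives DEFF 6.60 and 45%. Simulation at ICC 0.05 gave 31.6% for both tests.

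**Unequal clinic sizes (assumed coefficient of variation 1).** At m = 57 and ICC 0.01, simulation gave 18.6% and 17.5%.

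**Patient factors that vary within clinics, tested against an outcome.** Here DEFF is roughly 1 + (m − 1) × ICC of the factor × ICC of the outcome. With m = 57, an assumed factor ICC of 0.05 and outcome ICC 0.01: 1 + 56 × 0.05 × 0.01 = 1.028, a size of 5.3%. The problem nearly vanishes.

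**What it means in a table.** Table 2 lists over 20 clinic and care coordination factors. For 20 null factors against one outcome at m = 57 and ICC 0.01, the expected number significant at 5% rises from 20 × 0.05 = 1.0 to 20 × 0.117 = 2.3.

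**The case against.** The strongest reply is that nothing depends on these tests. They are labelled descriptive, inference is by mixed models with a clinic intercept, and Aim 1 is reported as estimates with 95% confidence intervals from those models. That stands, and it limits the importance of the point.

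Secondly, the plan gives the two tests only as examples, to be used where appropriate, and states no unit. A reader might infer that patient-level testing of everything is prescribed. It is not: clinic factors can validly be tested against the care model with the clinic as unit. But survey response and outcomes are recorded per patient, so patient rows are the natural reading there, and neither named test is appropriate for clustered patients when the other variable is set by clinic.

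Thirdly, a reader might infer that falsely significant imbalances will decide which confounders enter the models. The documents do not support this. Section 7.3.8 sets no significance threshold, and Section 7.3.1 has covariates "selected based on a combination of substantive knowledge, empirical evidence, and model fit statistics", with forward stepwise selection. Bivariate results may inform that judgement, but no rule makes them do so. Moreover, with non-random allocation a chance imbalance in a prognostic factor can still confound, and a liberal screen errs toward extra adjustment. This is a further reason to look at the size of an imbalance and not at its p-value.

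Fourthly, a reader might infer that the unadjusted columns of Section 7.3.3 will rest on these tests, or that the care models will be compared on outcomes by Fisher's exact or Kruskal-Wallis. Section 7.3.3 names no method, and single-factor mixed models would fit its wording. Section 7 pairs factors with outcomes and does not explicitly list a test of care model against outcome.

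**Conclusion.** The point holds in a limited form. As written, Section 7 allows unadjusted tests on patient rows where one variable is fixed within clinics. At the plan's ICC of 0.01 and equal clinic sizes, the false-positive rate is then about 12 to 13% in the full cohorts, 8% for claims and 6 to 6.5% for survey outcomes, against a nominal 5%. Describing the inflation as severe throughout would go beyond the documents: rates of 31% or more need an ICC of 0.05 or above, which is an assumption, although stronger clustering of baseline characteristics is compatible with Section 7.3.6.5. Very unequal clinic sizes would also raise the rates. Patient factors that vary within clinics are little affected when tested against outcomes.

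The primary and secondary mixed-model results are not directly affected. What needs correcting is the reported p-values in the descriptive balance, survey-response and unadjusted tables, and any weight placed on them in assessing confounding. The change is worth making before those tables are produced.

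**What to change.** Amend the opening paragraph of Section 7 as follows.

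- Describe balance between care models by standardised differences, at patient and at clinic level, without p-values, and refer to these in Section 7.3.8, item 3.
- For patient-level bivariate tests against the care model, survey response or outcomes, use a single-factor version of the Aim 1 model with the clinic random intercept, or a cluster-robust test. State that the unadjusted comparisons in Section 7.3.3 come from the same models.
- Keep Fisher's exact and Kruskal-Wallis only where the clinic is the unit of analysis, for example clinic characteristics by care model, and state the unit in each table. The unit matters: a clinic factor copied onto 57 patient rows has ICC 1 and DEFF 57, and would be tested at a true size of about 80%.

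The cost is a few sentences in the SAP and some extra model runs on data already held. For scale, with 57 per clinic and ICC 0.01, a valid test needs |z| above 1.96 × √1.56 = 2.45 where the unadjusted test uses 1.96, so some associations will lose nominal significance.

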7.1 Outcomes

Our outcomes fall into three categories: care quality (drawing on statewide quality measures reported by MNCM), utilization (drawing on insurance claims data collected by payor partners), and patient-centered/patient-reported outcomes (collected directly from care coordination patients who agree to complete a survey). Section 5 describes how data will be collected. **Table 3** summarizes study outcomes. Timing of outcome assessment will be anchored by the first date of receiving care coordination services, thereby creating a consistency across comparators and mitigating potential sources of bias due to timing. Modifications to these definitions and planned analysis may arise if certain data quality and availability thresholds are not met.

Table 3: Study Outcomes

Outcome measure	Definition	Source	Primary/ Secondary	Follow-up duration

Care Quality from the healthcare professional perspective				
Overall care quality	Composite measure of overall quality comprised of the percentage of all care quality outcomes in which a patient qualifies and meets quality criteria for	MNCM quality measures	Primary	12m
Asthma care at goal*	Asthma pts. with asthma control test (ACT) score >19	MNCM quality measures	Secondary	12m
Breast Cancer Screening* (up-to-date)	Women 50-74 yrs old who received a mammogram in the past one year	Health plan claims	Secondary	12m
Chlamydia Screening* (up-to-date)	Female patients 16-24 yrs old who had a screening test for chlamydia	Health plan claims	Secondary	12m
Colorectal Cancer Screening* (up-to-date)	50-75 yr old pts. up-to-date for an approved screening test	MNCM quality measures	Secondary	12m
Depression improvement*	PHQ-9 score <5 for test nearest to end of follow-up period	MNCM quality measures	Secondary	12m
Diabetes care at goal (including component measures)	All-in-one measure of control A1c, blood pressure, statin use, & smoking	MNCM quality measures	Secondary	12m
Vascular care at goal (including component measures)	All-in-one measure of control of blood pressure, statin use, & smoking + aspirin use in patients with vascular disease	MNCM quality measures	Secondary	12m
A1c control*	Hemoglobin A1c ≤ 7% in patients with diabetes	MNCM quality measures, clinic data	Secondary	12m
A1c level	Hemoglobin A1c in patients with diabetes	MNCM quality measures, clinic data	Secondary	12m
Aspirin or anti-platelet use*	Aspirin use in patients with vascular disease unless with contraindication or exception	MNCM quality measures	Secondary	12m
Blood pressure control*	< 140/90 mm Hg	MNCM quality measures, clinic data	Secondary	12m
Blood pressure level	Systolic and diastolic blood pressure (mm Hg)	MNCM quality measures, clinic data	Secondary	12m

Body mass index	kg/m ² (Primary Cohort only)	MNCM quality measures, clinic data	Secondary	12m
Low-density lipoprotein level	mg/dL in patients with diabetes or vascular disease	MNCM quality measures	Secondary	12m
Statin use*	Current statin use in patients with vascular care unless with contraindication or exception	MNCM quality measures	Secondary	12m
Tobacco use*	Current tobacco use (tobacco includes any number of cigarettes, cigars, pipes, or smokeless tobacco) in patients with diabetes or vascular disease	MNCM quality measures	Secondary	12m
Utilization from the healthcare system perspective				
Emergency dept. visits	# of encounters with CPT-4 E&M codes (99281-99288) at emergency dept. site	Health plan claims	Primary	12m
Hospitalizations	# of hospital inpatient admissions ≥ 1 days	Health plan claims	Primary	12m
Hospital readmissions <30 days	# of hospital inpatient admissions ≥ 1 days following a prior hospitalization <30 days	Health plan claims	Secondary	12m
Primary care visits	# of encounters with CPT-4 E&M codes (99201-99215, 99381-99429) at primary care site	Health plan claims	Secondary	12m
Specialty care visits	# of encounters with CPT-4 E&M codes (99201-99215, 99381-99429, 99241-99245, 92920-93895) at primary care site	Health plan claims	Secondary	12m
Urgent care visits	# of encounters with CPT-4 E&M codes (99201-99215, 99381-99429) at urgent care site	Health plan claims	Secondary	12m
Substance use treatment	Substance use treatment indicated by HCPCS codes (H0005-H0029, H0047, H2034-H2036)	Health plan claims	Secondary	12m
# of chronic medications	# of distinct concurrent dispensed medications, combined across drug classes used for chronic conditions (e.g., hypertension, hyperlipidemia, diabetes, asthma, depression)	Health plan claims	Secondary	12m

Cost of medical care	Resource use x price index	Health plan claims	Secondary	12m
Patient reports from the patient/family perspective				
General health status	NHIS	Patient survey	Primary	6m-18m
Rating of primary care clinic	CG-CAHPS	Patient survey	Primary	6m-18m
Access to care	CG-CAHPS	Patient survey	Secondary	6m-18m
Rating of care coordinator	CG-CAHPS (adapted)	Patient survey	Secondary	6m-18m
Shared decision making	3-item CollaboRATE ⁴⁴	Patient survey	Secondary	6m-18m
Perceived care integration	4-item IntegRATE ⁴⁵	Patient survey	Secondary	6m-18m
Going without care due to cost	National Health Interview Survey	Patient survey	Secondary	6m-18m
Out-of-pocket medical costs	Medical Expenditure Panel Survey	Patient survey	Secondary	6m-18m
Medication and care burden	Modified subset of 7-item Treatment Burden Questionnaire (TBQ) ⁵⁰	Patient survey	Secondary	6m-18m
Social needs	Modified subset of 10-item CMS HRSN Screening Tool ⁵¹	Patient survey	Secondary	6m-18m
Insurance coverage	State Health Access Data Assistance Center (SHADAC) Coordinated State Coverage Survey	Patient survey	Secondary	6m-18m

* Subcomponent of overall care quality composite outcome

Notes: MNCM = MN Community Measurement; m = months.

[figure not shown]

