2.3 Study Outcomes

This study will evaluate comparative effectiveness measured across three outcome domains. The primary outcomes are identified by an asterisk:

Patient Care Quality	Control of blood pressure, cardiovascular disease, diabetes, asthma, and depression and cancer screening (from standardized state-wide quality measures) as well as a composite measure* of overall quality comprised of the percentage of all care quality outcomes for which a patient qualifies and meets quality criteria
Patient Healthcare Utilization	Rates of urgent care, emergency department visits*, and hospitalizations*, as well as primary care and specialty visits, and substance use programs (from claims data) as primary care and specialty visits, and substance use programs (from claims data). We will also use utilization data to estimate medical costs in U.S. dollars.
Patient-Reported Outcomes	Health status*, satisfaction with care*, clinician, access, and coordination, care integration, shared decision making, medication and care burden, change in insurance coverage, going without care due to cost or COVID-related problems, out-of-pocket medical costs, and changes in social needs (from patient surveys)

Please see **Table 3** in Section 7 (Analysis Plan) for detailed outcome definitions.

[figure not shown]
3 Study Design

This is an observational mixed-methods comparative effectiveness study of a natural experiment in which clinics have chosen one of two models of care coordination for their own reasons in order to comply with requirements for state certification as a medical home. We will also address the related important questions raised by our stakeholder partners about what specific components of coordination and the local context are important and for which patients and needs coordination is most helpful. We will combine patient survey data (post only) with claims and quality measures (pre/post) and clinic coordination information to evaluate study outcomes. We will also use interviews of patients and health care professionals to develop study instruments and to increase understanding and validation of outcomes.

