I	Health Plan	Product Type	
 • 1 = Commercial • 5A = Medicare Advantage • 5C = Medicare Cost • 6 = MSHO • 7A = Medicaid (MNCare) • 7B = Medicaid (PMAP) • 7C = Medicaid (Hennepin Health) • 8 = SNBC (Special Needs Basic Care) • 77 = Minnesota Senior Care Plus (MSC+) 	R	String; 2 digits	Blank fields
J	Health Plan	Insurance Plan Enrollment Start Date		R	mm/dd/yyyy or m/d/yyyy	Blank fields
K	Health Plan	Insurance Plan Enrollment End Date		R	mm/dd/yyyy or m/d/yyyy	Blank fields
L	Health Plan	Pharmacy Data availability	
 • 0=No • 1=Yes • Is pharmacy data available in the plan data warehouse? 	R	String; 1 digit	Blank fields

Professional Data File (HCFA 1500)

Standard claim form for physicians and other health care professionals.

Submit one line per patient per procedure claim. Patients may be listed in multiple rows for multiple procedure claims.

Element Order	Field Name	Details	Required or Situational	Format/Field Length	Error Causes
A	Study ID	Unique MNCARES assigned non-PHI study ID for patient	R	String; up to 10 characters	Blank fields
B	Claim ID		R		Blank fields
C	Provider First Name	Enter the first name of the provider.	S	String	
D	Provider Middle Name	Enter the middle name of the provider if it is recorded in the medical record.	S	String	
E	Provider Last Name or Facility Name	Enter the last name of the provider.	R	String	Blank fields Values outside allowable range
F	Provider Specialty Type	Enter the code that corresponds to the Provider's Specialty. Please refer to the Standard Medicare Taxonomy Codes .	R	String; up to 15 characters	Blank fields Values outside allowable range
G	Clinic Site of Service		R	Number; up to 2 digits	Blank fields Values outside allowable range
H	Start Date of service		R	mm/dd/yyyy or m/d/yyyy	Blank fields
I	End Date of service		R	mm/dd/yyyy or m/d/yyyy	Blank fields
J	Procedure Code	Enter the CPT/HCPCS code that corresponds to the procedure claim. Do not include modifiers.	R	String; 5 characters	Blank fields
K	Modifier(s)		S	String; 8 characters	
L	Units		R		Blank fields
M	Billed Charges	To be used only for calculation of Relative Value	R	Number, 2 digits	

Facility Data File (UB04)

Hospital and Facility Header File, one line per admission or bundle of outpatient services.

Element Order	Field Name	Details	Required or Situational	Format/Field Length	Error Causes

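### Table 3 restricts specialty care visits to primary care sites and gives them all the primary care codes, so the outcome counts every primary care visit and no specialty-site visit

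*Combined protocol and SAP*

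**What the plan says.** Three visit outcomes in the utilization block of Table 3 (Section 7.1) are defined by a list of procedure codes and a site:

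- Primary care visits: number "of encounters with CPT-4 E&M codes (99201-99215, 99381-99429) at primary care site".
- Specialty care visits: number "of encounters with CPT-4 E&M codes (99201-99215, 99381-99429, 99241-99245, 92920-93895) at primary care site". The part at issue is the ending, "99381-99429, 99241-99245, 92920-93895) at primary care site".
- Urgent care visits: number "of encounters with CPT-4 E&M codes (99201-99215, 99381-99429) at urgent care site".

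All three are secondary outcomes from health plan claims with 12 months of follow-up. Section 2.3 names the first two side by side ("as well as primary care and specialty visits, and substance use programs (from claims data") and sends the reader to Table 3 for the definitions. No other section defines a specialty visit.

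Appendix C requires two relevant fields in the professional claims file: a provider specialty code ("Enter the code that corresponds to the Provider's Specialty") and "Clinic Site of Service". Nothing in the plan says how either field identifies a specialty visit.

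**The concern.** The primary care and urgent care rows have identical codes and differ only in site, so site is what separates visit types in this table. The specialty row carries the primary care site. With the primary care codes also in its list, it takes in every primary care visit and shuts out the visits its label describes.

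The definition feeds many results. Section 7.3.1 analyses utilization outcomes both as any versus none and as counts, in each cohort, with a pooled cohort-by-model interaction test and, where data allow, 1-, 2- and 3-year estimates in the Historical cohort. Aims 2 and 3 reuse the outcomes, and Section 7.3.5 aggregates outcomes by clinic or organization for feedback to care systems.

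The direction of a finding is also at risk. Facilitating care by specialty providers is one of the coordination services listed in the organizational and care coordinator surveys. If one model moved patients from primary care to specialists seen elsewhere, the outcome as written would fall when specialty use had risen.

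**Working it through.** The plan gives no figure to reproduce, because the point concerns a definition. The check expands each row into pairs of code and site and compares the sets. Every integer in a printed range is counted, whether or not it is a code in use; this does not affect whether one set contains the other.

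**Inputs (Table 3)**

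| Range | Number of integers | Primary care row | Specialty row | Urgent care row |
|---|---|---|---|---|
| 99201-99215 | 99215 − 99201 + 1 = 15 | yes | yes | yes |
| 99381-99429 | 99429 − 99381 + 1 = 49 | yes | yes | yes |
| 99241-99245 | 99245 − 99241 + 1 = 5 | no | yes | no |
| 92920-93895 | 93895 − 92920 + 1 = 976 | no | yes | no |
| Site | | primary care | primary care | urgent care |

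**Set sizes**

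- Primary care row: 15 + 49 = 64 pairs.
- Specialty row: 15 + 49 + 5 + 976 = 1,045 pairs.

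**Comparisons**

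- Primary care pairs that are also specialty pairs: 64 of 64. The specialty row is a strict superset.
- Specialty pairs outside the primary care row: 1,045 − 64 = 981 (5 + 976), all at a primary care site.
- Specialty pairs at any other site: 0.
- Specialty pairs shared with the urgent care row: 0, because the sites differ.

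**Consequence for the outcome.** For one patient, let P be the primary care count and E ≥ 0 the number of encounters at a primary care site that qualify only through the added ranges. As written, the specialty count is S = P + E, so S ≥ P for every patient. In the any-versus-none version, any patient with a primary care visit is automatically positive for specialty care.

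For mean counts, let w be the share of S that is P in the reference group. The rate ratio for S is then

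RR_S = w × RR_P + (1 − w) × RR_E.

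As w approaches 1, the specialty result approaches the primary care result; for smaller w it is a mixture of the two. The documents give no claim frequencies, so w cannot be estimated. The pair counts show containment; they do not measure visit volume.

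**Effect of correcting the site.** With the code list unchanged and the site set to a specialty (non-primary-care) site, overlap with the primary care row falls from 64 pairs to 0, and overlap with the urgent care row stays at 0.

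**The case against.** The strongest reply is that this is an evident slip. The row is labelled as specialty care, it adds code ranges of its own, and it sits close to rows told apart by site, so the phrase was probably carried over from the primary care row. Section 6.4 calls for data dictionaries vetted by the study partners, including for the final analytic files, and a specialty variable that contained every primary care visit might be noticed there. That lowers the chance of the rule being programmed literally. It does not supply the intended rule. Because the office-visit codes are shared, site or specialty has to do the separating, and no text says how. An analyst would have to devise the rule, possibly with data in hand. The caveat in Section 7.1 does not help: "Modifications to these definitions and planned analysis may arise if certain data quality and availability thresholds are not met" covers shortfalls in the data, and this is neither a quality nor an availability problem.

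Three further points stand and limit the concern.

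- The specialty row is a superset of the primary care row, so a primary care effect would be mixed with the added codes, not copied exactly.
- Zero capture applies to specialty sites, not to all specialist care. Appendix E asks how many medical specialists work in each clinic, so some specialist encounters may take place at a primary care site and would be counted.
- The outcome is one of many secondary outcomes. The power statements in Section 7.2 do not use it, the primary utilization outcomes are emergency department visits and hospitalizations, and cost has its own definition.

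**Conclusion.** The concern holds. Read literally, the specialty definition contains 64 of 64 primary care code-and-site pairs and none at a specialty site. Each patient's specialty count is therefore at least the primary care count, and specialty-site visits are missed entirely. This follows from the wording of Table 3 alone. That the site phrase was carried over from the primary care row is an inference. The size of any distortion in the estimated model effect depends on the claims mix, which the documents do not report. The damage is confined to one secondary outcome and the analyses that reuse it. It should be corrected before the utilization variables are programmed, but no primary result depends on it.

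**What to change.** In the specialty row of Table 3, replace the primary care site with a non-primary-care specialty condition. Base it on Provider Specialty Type, supported by the site field; both are required in the Appendix C professional claims file. List the specialty codes treated as primary care, because the site field has no code list in the documents and may not separate the two settings by itself.

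Also state that each encounter counts in only one of the primary care, specialty and urgent care categories, and give the order of precedence. A site correction alone would not need this rule, but a definition based on provider specialty would: a specialist's encounter at an urgent care or primary care site could otherwise be counted twice.

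The cost is one revised row in Table 3, a short code list and a sentence on precedence, carried into the data dictionary. No new data are needed, and the sample size and primary analyses do not change.
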